## 1.2 SCHEMA

## 1.3 SCHEDULE OF ACTIVITIES (SOA)

Subjects:	All							Participating in Crossover *							All
Time Point Following:	Initial Treatment							Crossover Treatment							Initial
Time Point (Days):	0	1	7					0	1	7					
Time Point (Months):				1	2	3	4				1	2	3	4	12
Written Informed Consent	•														
Screening for eligibility	•														
Urine Pregnancy test ( as needed)	•							•							
Randomization	•														
Conscious sedation and study treatment	•							•							
Phantom Limb Pain (worst, least, average, current), NRS	•	•	•	•	•	•	•	•	•	•	•	•	•	•	•
Residual Limb Pain (worst, least, average, current), NRS	•	•	•	•	•	•	•	•	•	•	•	•	•	•	•
Patient Global Impression of Change Scale		•	•	•	•	•	•	•	•	•	•	•	•	•	•
Brief Pain Inventory Interference Scale	•	•	•	•	•	•	•	•	•	•	•	•	•	•	•
Non-Painful Phantom Sensations (# and duration)	•	•	•	•	•	•	•	•	•	•	•	•	•	•	•
Phantom Limb Pain (# and duration)	•	•	•	•	•	•	•	•	•	•	•	•	•	•	•
Residual Limb Pain (# and duration)	•	•	•	•	•	•	•	•	•	•	•	•	•	•	•

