# 6 STUDY INTERVENTION

## 6.1 STUDY INTERVENTION(S) ADMINISTRATION

### 6.1.1 STUDY INTERVENTION DESCRIPTION

For individuals of childbearing potential, a sample of urine will be collected before any study interventions to confirm a non-pregnant state.

**Treatment group allocation (randomization).** Participants will be allocated to one of two possible treatments groups:

1. *Cryoneurolysis*
2. *Sham procedure (Control)*

Randomization lists will be created using computer-generated tables by the Investigational Pharmacy (UC San Diego) in a 1:1 ratio and block sizes of 2. Treatment group assignment will be conveyed to the investigators in the form of sealed, opaque envelopes only by the treating investigator. Therefore, all investigators and participants will be masked to treatment group assignment, with the only exception being the investigator who performs the procedure (and will not have subsequent contact with the participant). ***This protocol will enable a randomized, observer- and participant-masked, sham/placebo-controlled study.*** It is impossible to mask the individual performing the cryoneurolysis procedure because the ice ball forming at the distal end of the probe—with *active* treatment—is clearly visible by ultrasound; and the lack of an ice ball for placebo participants is equally clear. It is essential to continuously visualize the probe and target nerve throughout the two freeze/thaw cycles to ensure the entire nerve diameter is adequately treated and remains relatively motionless. This cannot be achieved if the ultrasound is turned off during nitrous oxide administration to mask the provider; and we prioritize patient safety over masking of the physician administering the intervention. All participants will have a peripheral intravenous (IV) catheter inserted, standard noninvasive monitors applied (blood pressure cuff, pulse oximeter, 5-lead ECG), and oxygen administered *via* a nasal cannula or facemask. Midazolam and fentanyl (IV) will be titrated for patient comfort, while ensuring that patients remain responsive to verbal cues.

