The cryoneurolysis sites will be cleansed with chlorhexidine gluconate and isopropyl alcohol. ***The nerves treated will include the femoral, sciatic, obturator, and lateral femoral cutaneous.*** Each nerve will be visualized using ultrasound, a skin wheal of local anesthetic will be raised inferior to the transducer to anesthetize the skin and then the track towards the target nerve. The probe will then be inserted adjacent to the target nerve. The cryoneurolysis machine (CryoCare, Varian Medical Systems, Palo Alto, California) uses argon for the freeze cycle and helium to help decrease the thaw period duration. The cryoneurolysis device will be triggered using 1 cycle of 5.5-minute argon activation (2000-2500 PSI and 100% power) followed by a 30-second helium defrost. The Varian machine provides its own timer so that the gas cycle timing is precise to the second. This may be repeated, as necessary, to ensure the entire cross-section of each nerve is fully treated.

**Active Cryoneurolysis.** For participants randomized to active treatment, the probe placed in the patient will be triggered and the argon (and helium) passed through the probe and then back into the machine, and finally vented out from the console. This will result in a freeze-thaw cycle.

**Control.** For participants randomized to sham treatment, the probe in the patient will simply not be activated; instead, a second probe that is not inserted in the patient will be triggered which will create the same visual and auditory cues as for the active participants retaining the masked feature. The investigator administering the study intervention will activate the correct probe depending on the treatment group assignment. Therefore, all investigators and participants will be masked to treatment group assignment, with the only exception being the unmasked investigator who performs the procedure (and will not have subsequent contact with the participant).

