## **7 STUDY INTERVENTION DISCONTINUATION AND PARTICIPANT DISCONTINUATION/WITHDRAWAL**

### **7.1 DISCONTINUATION OF STUDY INTERVENTION**

Cryoneurolysis procedure will be discontinued if the participant requests during the procedure. Additionally, if the investigator feels that continuing with the intervention would adversely affect the patient's health—such as a hemorrhage—the intervention might be discontinued.

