### 9.4.5 BASELINE DESCRIPTIVE STATISTICS

Balance on baseline covariates will be assessed using absolute standardized difference (ASD) i.e., difference in means or proportions divided by the standard deviation.  $ASD > 0.1$  will be considered to indicate imbalance, and these variables will be adjusted for in the statistical analyses. Analyses will be carried out using modified intention-to-treat i.e., patients who received any study treatment will be analyzed according to the group they were randomized to.

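### The modified intention-to-treat rule drops randomized participants on an undefined criterion, and nothing prevents the decision behind an exclusion from being made with knowledge of the arm

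*Combined protocol and SAP*

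**What the plan says.** **Analysis set.** The only definition stands in section 9.4.5, under baseline descriptive statistics: "patients who received any study treatment will be analyzed according to the group they were randomized to". Section 9.3, which is headed as the place for analysis populations, gives only counts (20 for analysis, 5 extra for dropouts, 25 in total).

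**Start of treatment.** No section says when study treatment begins. The schedule in section 1.3 has a single row, "Conscious sedation and study treatment", and does not separate sedation, local anesthetic, probe insertion and gas activation.

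**What each arm receives (section 6.1.1).** In the active arm "the probe placed in the patient will be triggered". In the control arm "the probe in the patient will simply not be activated; instead, a second probe that is not inserted in the patient will be triggered". The control is itself called a treatment ("For participants randomized to sham treatment").

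**Allocation.** Section 6.1.1 specifies a 1:1 ratio in blocks of 2, and says: "Treatment group assignment will be conveyed to the investigators in the form of sealed, opaque envelopes only by the treating investigator". It gives no time of opening relative to sedation or probe placement. The investigator who performs the procedure is the one person on Day 0 who is not masked.

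**Stopping.** Section 7.1 allows a stop at the participant's request, and also "if the investigator feels that continuing with the intervention would adversely affect the patient's health". It does not say whether that investigator is the operator or a masked colleague.

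**The concern.** Membership of the analysis set depends on something that happens after randomization. That is harmless if the event cannot be influenced by knowledge of the arm and is defined identically in both arms. The plan secures neither condition.

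The operator may already know the assignment when a procedure is called off, and nothing assigns that decision to someone masked. Because the qualifying step is not named, whoever builds the analysis set must decide whether a participant with a probe in place but nothing yet triggered was treated. That judgement could fall differently by arm, since an active participant at that point has had no freeze, whereas a sham participant has already had everything that sham puts into the body.

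The comparison would then no longer be between the groups as randomized. This matters in a pilot too. The stated purpose is to estimate the treatment effect so that a definitive trial can be sized, and section 9.1 still sets P < 0.05 for the primary outcome.

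**Working it through.** **1. The plan's own figure.** 20 + 5 = 25, as stated; the implied dropout allowance is 5/25 = 20%. The sample is one of convenience, with no SD, effect size or power, and no rate of stopped procedures is given. Everything in steps 4 to 6 therefore rests on assumed inputs.

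**2. Which stops lead to exclusion.** The rule asks for any study treatment, and four nerves are treated. A participant stopped after treatment of the first nerve stays in. Only a stop between randomization and the first qualifying step removes anyone.

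**3. How that stop is classified under each possible starting step.**

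| Treatment starts at | Probe placed, nothing triggered: active | Same stop: sham |
|---|---|---|
| Sedation | in | in |
| Probe insertion | in | in |
| Triggering the assigned probe (inserted or second) | out | out |
| Freeze in active, insertion in sham | out | in |
| Gas through the inserted probe | out | out, and no sham participant ever qualifies |

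The first three readings treat the arms alike. The fourth does not. The fifth cannot be intended, because it would empty the control arm. The text does not choose among them.

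**4. Shift in an arm mean.** Let n be the arm size, k the number excluded from that arm, and d the difference between the mean of those excluded and the mean of those retained. The full mean equals the retained mean plus (k/n) × d, so the exclusion shifts the arm mean by (k/n) × d.

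- n = 10, k = 1: d = 3, 4, 5 gives 0.3, 0.4, 0.5 NRS points.
- n = 10, k = 2: d = 1, 2, 3 gives 0.2, 0.4, 0.6 points.
- n = 12, k = 1: d = 1, 2, 3 gives 0.08, 0.17, 0.25 points.

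**5. Against the noise.** The standard error of the difference with 10 per arm is SD × √(2/10). For an assumed SD of 2 to 3 points this is 0.89 to 1.34 points, which exceeds every shift above.

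**6. Type I error.** Two-sided t-test at 0.05, no true effect, exclusions from one arm only, 100,000 simulated trials per setting:

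| Exclusion and outcome | n = 10, k = 1 | n = 10, k = 2 | n = 12, k = 1 | n = 12, k = 2 |
|---|---|---|---|---|
| Unrelated | 0.050 | 0.050 | 0.050 | 0.050 |
| Correlation 0.3 | 0.051 | 0.054 | 0.052 | 0.055 |
| Correlation 0.5 | 0.055 | 0.065 | 0.056 | 0.064 |
| Worst outcome always removed | 0.073 | 0.116 | 0.071 | 0.113 |

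At correlations of 0.3 to 0.5 the mean shift is 0.04 to 0.16 SD.

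**7. Predictability.** In a block of 2 the second assignment is the opposite of the first. An operator who knows the block size and the previous assignment can infer every second one before any envelope is opened.

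**The case against.** A reader might infer that the rule itself classifies the same early stop differently in active and sham. The documents do not support that. Section 9.4.5 uses one wording for both arms, and section 6.1.1 gives both arms a trigger step, since in sham a second probe is fired. A sham participant stopped before that step has not completed the sham any more than an active participant has completed the freeze. The different treatment by arm arises only under one of several possible definitions. What stands is that the term is open, so nothing prevents that definition from being used.

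A reader might also infer that the operator does stop procedures knowing the arm. That is not shown. Section 7.1 does not name the operator, a stop requested by the participant comes from a masked person, and the order of rows within the Day 0 column of the schedule does not fix when the envelope is opened. What stands is that no safeguard is written down.

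The remaining objections concern size, and they are fair. Pain or bleeding after the first nerve has been treated excludes nobody. There may be no qualifying stop at all, in which case the effect is nil. Plausible shifts are smaller than the standard error. Section 9.4.9 calls all analyses exploratory, and participants who are kept are analysed as randomized. These points limit the urgency. They do not give a reason to drop randomized participants when outcome data can be had from them at almost no cost.

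**Conclusion.** The concern holds in a limited form. The plan excludes randomized participants on an undefined post-randomization criterion and leaves room for the decision behind the exclusion to be made with knowledge of the arm.

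The likely effect is modest. With an assumed 0 to 2 exclusions and about 10 per arm, one exclusion moves an arm mean by d/10. Type I error stays at 0.051 to 0.065 for correlations of 0.3 to 0.5 between exclusion and outcome. Values of 0.07 to 0.12 need the worst outcomes always to be the ones removed. The number of stops, d, the SD and the correlations are all assumptions.

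The change is worth making because it is nearly free and because the estimate is meant to size the next trial.

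**What to change.** **Sections 9.3 and 9.4.5.** Replace the modified intention-to-treat rule with: all randomized participants are analysed in the group assigned. Place it in section 9.3. State that a participant whose procedure is stopped early remains in the existing masked telephone follow-up unless consent is withdrawn. Section 7.3 already commits to contact attempts for 12 months, but section 7.2 also lets an investigator withdraw participants, so this should be explicit. Report every post-randomization stop by arm with its reason. If a treated-only analysis is kept as a supplement, define study treatment by a step that is identical in both arms.

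**Section 6.1.1.** State that the envelope is opened only after the first probe is placed and immediately before activation, and that this is the moment of randomization. Earlier stops then meet the screen-failure definition in section 5.4. Late opening is not enough on its own while the second assignment of each pair can be inferred, so also replace the fixed blocks of 2 with concealed, varying block sizes.

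**Cost.** A few sentences; no added staff, visits or equipment. Both probes must be set up before the arm is known, and varying blocks may leave the arms slightly unequal. A retained untreated participant dilutes the estimate a little: one of 10 active participants responding as sham reduces a true difference Δ to (9/10) × Δ = 0.9Δ.

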### 9.4.6 PLANNED INTERIM ANALYSES

None.

### 9.4.7 SUB-GROUP ANALYSES

None.

---

#### 9.4.8 TABULATION OF INDIVIDUAL PARTICIPANT DATA

Individual patient data will not be reported, only aggregate.

---

#### 9.4.9 EXPLORATORY ANALYSES

This is a pilot study and therefore all of the analyses will be exploratory requiring confirmation in a subsequent adequately-powered clinical trial.

---

### 10 SUPPORTING DOCUMENTATION AND OPERATIONAL CONSIDERATIONS

---

#### 10.1 REGULATORY, ETHICAL, AND STUDY OVERSIGHT CONSIDERATIONS

---

##### 10.1.1 INFORMED CONSENT PROCESS

**Enrollment.** Study subjects will be identified from 3 sources:

1. **Clinics.** The investigation team will meet with clinic (amputee-specific, surgical, and chronic pain) personnel to both in-service them on the study protocol as well as provide Institutional Review Board-approved written information describing the investigation that may be given to prospective subjects during clinic visits. Clinic patients will come into contact with their healthcare providers during regularly scheduled clinic visits, and these providers will briefly describe the study and offer written information to patients with phantom limb pain who voice interest in the study. Patients who are interested in the study will be required to give permission for a research coordinator to contact them to adhere to Health Insurance Portability and Accountability Act (HIPAA) requirements.

2. **Advertisements.** The Primary Investigator will place Institutional Review Board-approved study advertisements within print and web-based publications that are frequently read by the target population. Additionally, we will provide similar Institutional Review Board-approved advertising material to the leaders of local and regional amputee focus/support groups. Individuals who are interested in the study will be directed to contact the study investigators or research coordinators for a thorough description of the study purpose and protocol. In addition, Institutional Review Board-approved advertisements will be placed, and a study-specific information page created within Facebook, which has over 1-billion members. Of note, the United States Army, Navy, Air Force, and Marines all have dedicated Facebook information pages. Information on how to volunteer for the study will also be placed in relevant Twitter (now “X”) feeds, such as the Clinical Trial Spotlight San Diego, and Clinical Connection, free portals for finding clinical trials.

3. **ClinicalTrials.gov.** The trial will be prospectively registered on the ClinicalTrials.gov website. One of the main purposes of trial registries is to provide the general population access to available ongoing

investigations. Contact information for the site directors will be included on the website so that prospective subjects may receive a thorough description of the study purpose and protocol.

Once a prospective subject contacts an investigator or research coordinator by telephone or email, they will be provided information on the study purpose and protocol, as well as have any questions answered. Inclusion/exclusion criteria will be reviewed and documented on a form to identify subject eligibility according to these criteria. If a prospective subject is excluded for any reason, the reason for exclusion will be recorded, but no patient identifying information will be recorded. Candidates who meet inclusion and exclusion criteria and desire study enrollment will be scheduled for their initial study treatment. Written informed consent will be attained prior to any measurements or procedures prior to the initial treatment (see below for a detailed description of the informed consent process).

We are requesting a partial waiver of HIPAA authorization for recruitment as protected health information will be reviewed to ascertain appropriate inclusion/exclusion criteria:

1. These procedures are minimal risk to the potential participants as we are asking focused medical questions (e.g., where is your amputation?) and are not recording the responses—they are used to simply ascertain whether or not the prospective participant meets criteria.
2. A waiver of HIPAA authorization for recruitment would not adversely affect the rights and welfare of the potential participants as we are asking focused medical questions (e.g., where is your amputation?) and are not recording the responses—they are used to simply ascertain whether or not the prospective participant meets criteria.
3. This clinical trial could not be practicably carried out without the waiver because we must ascertain inclusion/exclusion criteria before the prospective patient has travelled to the medical center. If they meet criteria, then they can decide whether or not to schedule the intervention; and we will collect written, informed consent as documented with an IRB-approved ICF at the beginning of their visit and prior to any questionnaires or procedures.
4. After prospective participants are contacted, if they would like to participate, they will receive written, informed consent using an IRB-approved informed consent form.

These procedures would also include access to PHI, so we request a partial waiver of HIPAA authorization for recruitment to be granted:

1. Identifiers will include the potential participant's age, level of amputation, pain levels, and willingness to avoid both changes to their analgesic regimen as well as elective surgical procedures from 1 month prior to and at least 4 months following the initial cryoneurolysis procedure. In addition, we will inquire about any allergy to amide local anesthetics, pregnancy, incarceration, ability to read English (for the ICF), weight and contraindications specific to cryoneurolysis such as a localized infection at the treatment site or Reynaud's syndrome. This information will not need to be recorded in hard-copy format. If the patient does not participate, then there will be no record of PHI specifically for study

purposes whatsoever. If the patient does participate, then PHI will be recollected following written, informed consent.

2. This clinical trial could not be practicably carried out without the waiver because we must ascertain inclusion/exclusion criteria before the prospective patient has travelled to the medical center. If they meet criteria, then they can decide whether or not to schedule the intervention; and we will collect written, informed consent as documented with an IRB-approved ICF at the beginning of their visit and prior to any questionnaires or procedures.

3. The privacy risk to individuals whose PHI will be used is minimal since we will not record any PHI specifically for study purposes until after written, informed consent is provided. The anticipated benefit to participants is a chance of improving their pain control if they are randomized to active treatment.

4. PHI that will be evaluated includes the items listed in #1 above.

An investigator or research coordinator will review the study protocol in detail with interested prospective participants; and, for patients desiring participation, written, informed consent will be obtained prior to any measurements, data collection, and/or interventions. The method of documenting informed, written consent will be IRB-approved consent forms. Vulnerable populations will not be enrolled.

Once a prospective participant contacts (or gives permission to be contacted by) an investigator or research coordinator, they will be provided information on the study purpose and protocol, as well as have any questions answered. Candidates who meet inclusion and exclusion criteria and desire study enrollment will be provided with written informed consent prior to any measurements or procedures prior to the intervention. The Principal Investigator is responsible for ensuring that written, informed consent is obtained from every participant. Clinical research coordinators will be specifically trained by the Principal Investigator to provide informed consent followed by documentation of informed consent using an Institutional Review Board-approved informed consent form. This will occur in private patient care areas, so that participants may feel comfortable asking questions.

We do not foresee any issues relevant to the mental capacity of the potential participants. Written, informed consent will be attained prior to any study procedures or measurements; and participants will not receive procedure-related sedation until following the written, informed consent process is completed. Participants will be provided privacy and time for decision making both in the study description/explanation telephone call to the site director or research coordinator, as described above; and also the day of the initial treatment using a private patient care area to again review the study, informed consent form, and answer any remaining questions. As noted previously, participants may speak with an investigator by telephone from initial contact through the morning of treatment; and will have access during and following the treatment(s) with cellular phone and pager numbers provided upon discharge.

Surrogate consent will not be accepted; therefore, if patients cannot provide consent on their own, they will not be offered study enrollment. Consent by an individual's Legally Authorized Representative will be unacceptable for study enrollment.

If a protocol amendment is required, then the ICF may need to be revised to reflect the changes to the protocol. If the ICF is revised, it must be reviewed and approved by the UCSD Human Research

Protections Program and signed by all participants subsequently enrolled in the clinical study, as well as those currently enrolled in the clinical study as applicable.

---

